This study occurs within the Northwestern Medicine health care system.

PRÉCIS

Study Title

Behavioral Economic Applications to Geriatrics Leveraging Electronic Health Records (BEAGLE)

Objectives

The main intent of this study is to determine whether an intervention comprised of 3 electronic health record (EHR) nudges designed using behavioral economic concepts reduces rates of over-prescribing in 3 clinical areas: prostate screenings, urinary testing for non-specific reasons female patients, and treatment for diabetes mellitus (DM). Our primary hypothesis is that practices randomized to receive these nudges will have lower over-prescribing rates in these 3 domains compared to control practices.

Design and Outcomes

We will conduct a multi-site cluster randomized trial of a behavioral intervention targeting overuse of prostate screening, urinary testing, and treatment for diabetes in geriatric patients, with practice as the unit of randomization.

The 3 co-primary outcomes are measured at the patient level, and capture whether an eligible patient received unnecessary treatment for a particular measure. We will report marginal monthly rates of each outcome. These include:

1. Ordering of prostate specific antigen (PSA) for prostate cancer screening in adult men aged 76 years and older
2. Ordering of urinalysis or urine cultures (UA/UC) for non-specific reasons to identify bacteriuria in women aged 65 years and older
3. Overtreatment of diabetes (DM) with insulin or oral hypoglycemic drugs in adults aged 75 years and older.

In the main analysis, we will compare a 12-month historical period to an 18-month intervention period. In subsequent secondary analyses to determine persistence of study effects, we will track all 3 co-primary outcomes for another 12 months after the intervention ceases.

Interventions and Duration

We will randomize clinics to either a brief education arm (clinicians at those clinics receive an invitation to an online education module) or brief education plus 18 months of clinical decision support within the EHR for the three clinical topics above.

The intervention period will be 18 months long, followed by an additional 12 months of data collection to assess persistence of study effects. We will also use data from a 12 month historical baseline period immediately prior to the start of the intervention period.

Sample Size and Population

We will recruit clinicians (physicians, advance practice nurses, and physician assistants) from 60 primary care clinics (internal medicine, family medicine and geriatrics) affiliated with Northwestern Medicine. Approximately 350 eligible clinicians will be recruited for this study.

We will randomize practices to intervention or control (1:1 allocation) using a constrained randomization algorithm, to achieve balance between study arms on baseline clinic characteristics.

1. STUDY OBJECTIVES

1.1 Primary Objective

Here, our primary aim is to evaluate the effects of an electronic health record (EHR) nudge designed to reduce over testing and treatment in geriatric patients for 3 clinical issues using a pragmatic cluster randomized controlled trial. We will measure the impact on validated quality measures associated with each of the 3 types of ‘nudge interventions’ and indicators of patient safety. The 3 clinical areas targeted by this nudge are:

- 1) Ordering of prostate specific antigen (PSA) for prostate cancer screening in adult men aged 76 years and older
- (2) Ordering of urinalysis or urine cultures (UA/UC) for non-specific reasons to identify bacteriuria in women aged 65 years and older
- (3) Overtreatment of diabetes (DM) with insulin or oral hypoglycemic drugs in adults aged 75 years and older.

1.2 Secondary Objectives

1.2.2. We plan to evaluate the persistence of any effects observed in Aim 1 by extending the analysis to include another 12 months of follow-up data.

1.2.1 Using a clinician survey administered twice – once pre-intervention roll-out and once at the end of the intervention period, we will measure the impact of our intervention on clinician attitudes.

2. BACKGROUND AND RATIONALE

2.1 Background on Overtreatment and Unnecessary Testing in Geriatric Populations

Despite strong recommendations from the American Geriatrics Society as part of the Choosing Wisely Initiative, sometimes clinicians do not follow best practices regarding ordering testing and treatments for their older adults that may lead to patient harm. These include: (1) testing and treatment for asymptomatic bacteriuria (ASB) in older women, (2) prostate specific antigen (PSA) screening in older men without prostate cancer, and (3) aggressive treatment with insulin or an oral hypoglycemic for older patients with type 2 diabetes.

Clinical decision support nudges, informed by behavioral economics and social psychology and delivered via EHRs, are promising strategies to reduce the misuse of services. Behavioral economics-informed interventions influence conscious and unconscious drivers of clinical decision making, are low cost to implement and disseminate, and can be incorporated into existing delivery systems. Our team has successfully employed these methods to the overuse of antibiotics for acute respiratory infections and has the necessary expertise in primary care practice, geriatrics, health informatics, social psychology, quality improvement, pragmatic trials and performance measurement to make this project a success. As our population continues to age, effective strategies to improve clinical care of older adults by reducing misused testing (e.g., urinalysis for ASB, prostate cancer screening with PSA) and treatment (e.g., overly-intense treatment of diabetes with insulin or other oral hypoglycemic) are critically needed.

2.2. Study Rationale

Preliminary data. This study builds on a pilot study conducted at Northwestern University by the same study team, which was funded by the National Institute on Aging (R21 #____; clinicaltrials.gov identifier NCT03704389). The EHR nudge used here, presented as clinical decision support prompts, were designed and pilot tested as part of that study.

During 2017-2018, our team interviewed NM primary care physicians caring for older adult patients to identify potential drivers of overuse of testing and treatment. Clinician participants reported knowledge of the Choosing Wisely recommendations (e.g., “We’ve always known to be a little more lenient for elderly patients because of hypoglycemia and falls...”), a reliance on patient preference (e.g., “Some patients are very insistent or expectant that they would want to continue to get testing”), clinical uncertainty and an underestimation of harms (e.g., “Don’t want to over test her, but at the same time if she has treatable UTI want to treat her to get her some relief.”). Additionally, we found that clinicians often perceive discussions with patients about not ordering tests or treatments to be time consuming (e.g., “After long discussion, seems overwhelming majority of patients want to do the test. Given limits of time we have, I’ve been less detailed in discussion...”). Finally, the theme of clinical inertia or resistance to change was present (e.g., “If this patient is doing well, I might leave it [diabetes treatment] alone.”)

In fall 2018, we used data from these interviews and worked with clinical and decision science experts to design a nudge comprised of three clinical decision support interventions. The study team extensively reviewed the language and programming decisions prior to launching a pilot test of these interventions in January 2019. We consented and enrolled fourteen Northwestern Medicine primary care physicians to receive clinical decision support within NM’s Epic electronic health record (EHR) when conditions within their patient’s chart met nudge trigger eligibility criteria. Images of the 3 best practice advisories (BPAs) tested in the pilot intervention are included as Protocol Supplement 1 (pg. 2-3). The pilot study ran for six months between January-July 2019. We did not receive any clinician complaints regarding the interventions during the study period. In June 2019, we fielded a clinician survey to collect their feedback on their experience with study nudges. We will use the three interventions in this randomized controlled trial. During the R21 pilot study, the PSA alert fired 15 times, in 2 cases (13%) the test was not done and in 3 (20%) cases the test was ordered and an exception added to the report. The UA/UC alerts fired 34 times and in 21 cases (62%) the test was not ordered. Finally, the DM alert fired 93 times and on chart review 34% of patients whose clinician received DM CDS had diabetes therapy reduced during the pilot period.

Rationale for Accountable Justification.

Asking clinicians to provide an accountable justification for their ordering action that is not consistent with professional guidelines or best practices may reframe the behavior as non-normative by requiring the clinician to supply in the EHR a justification that becomes part of the record when the clinical action is taken. In addition to changing perceptions of what is normative behavior, entering a note that will go into the patient record may engage feelings of social accountability that promote more careful reflection.

3. STUDY DESIGN

The Behavioral Economic Applications to Geriatrics Leveraging Electronic Health Records (BEAGLE) trial is a single site, cluster-randomized controlled trial with practice as the unit of randomization. The primary aim is to test the ability of an intervention based on behavioral economic principles to reduce the

rates of commonly occurring inappropriate testing and treatment in geriatric patients across 3 domains: PSA, UA/UC, and DM. We will randomize practices using a 1:1 allocation; clinicians at intervention practices will receive the intervention when an eligible patient is seen. If physicians at intervention clinics wish to override the clinical decision support tool, they will need to provide justification that appears in the patient's EHR (accountable justification). Clinicians at control practices will receive a one-time education module about the risks of over-treatment and testing in these areas.

We will enroll approximately 350 clinicians from 60 participating primary care clinic sites and collect baseline data for the 12 months leading up to the intervention start (monthly data collected using a look-back window of 12 months). All clinicians will receive a one-time education module about the risks of over-treatment and testing in these areas at the time of consent and enrollment. Clinician surveys will be administered at the time of enrollment and after the intervention is completed. The 3 co-primary outcomes are quality measures [detailed below in section 6]. Secondary outcomes are patient safety measures [detailed below in section 6]. The 18-month intervention period will be followed by a 12-month follow-up period to measure persistence of effects after interventions end. Patient-level data from EHRs at participating practices were abstracted at 3 points [detailed below in section 11].

4. SELECTION AND ENROLLMENT OF PARTICIPANTS

This clinical trial will be conducted at 60 clinics within Northwestern Medicine: Northwestern Medical Group in the North and Central regions and Regional Medical Group located in the western and northwestern Chicago suburbs. Leadership for these regions endorsed the system-wide conduct of this trial and its performance with a waiver of informed consent.

4.1 Clinic Eligibility

Practices that deliver outpatient primary care and include internal medicine, family medicine or geriatrics physicians or advanced practice providers will be included in this study. We will exclude practices that only have residents or only provide emergency care.

4.2 Patient eligibility

All patients aged 65 years and older will be included in the overall study patient population. We will assess study outcomes for all clinics, clinicians and individual patients who meet the pre-defined study eligibility criteria for each measure.

Co-Primary Outcome	Eligibility Criteria
PSA	All adult men aged 76 years and older with a visit to a participating primary care or geriatrics NM clinic between September 1, 2018 – February 28, 2023
DM	All adults aged \geq 75 years old with a visit to a participating primary care or geriatrics NM clinic visit between September 1, 2018 – February 28, 2023
UA/UC	All adult women aged 65 years and older with at least one primary care, geriatrics, or immediate care NM visit between September 1, 2018 – February 28, 2023

Note: all subjects over the age of 89 years will be aggregated into a single category. We will obtain these outcomes by queries of the NMEDW. Some data are prospective in that they do not exist at the time of

IRB submission but retrospective in that we will only have access to them after collected in NM Epic as part of routine care delivery.

5. STUDY INTERVENTIONS

5.1 Definitions of Study Interventions

Clinician education (control). An interactive educational module (15-20 minutes) covering the three targeted areas of overuse.

Clinical decision support plus clinician education (intervention).

Best Practice Advisories were programmed into Epic to present content to the clinician and feature functionality to add content to the encounter documentation. Clinicians attributed to clinics in the ‘CDS intervention + Education’ arm receive CDS alerts when conditions within a chart meet triggering criteria. For example, a CDS alert appears when a clinician places an order for a PSA test when the patient meets qualifying criteria (e.g., ≥ 76 years old, no prior prostate cancer). The CDS alerts encourage the clinician to cancel the order in the cases of PSA and urine testing or to decrease diabetes medication in the case of diabetes overtreatment (Table 1); however, they do not restrict clinical decision making in any way. If the clinician proceeds with the order for the PSA, urinalysis, or urine culture they are asked to enter text justifying the order. This justification is then included within the encounter report, visible to any clinician within the chart, under a heading titled ‘Testing Justification’. If the clinician does not enter a justification, the note “No justification given” is included in the encounter report.[9, 10] Images of the CDS presented to the clinicians for each alert and triggering criteria are included in the supplemental material. The EHR programming logic used in the pilot study was re-tested for this trial.

5.2 Administration and Duration of Interventions

The clinician educational module will be administered by the study team. The nudges will be delivered via NM’s instance of Epic and administered by NM IT.

The intervention period will be 18 months in length for all participants. We will continue to collect data on all study outcomes for 12 months after the intervention ends to measure persistence of effects. The pre-intervention baseline period will be 12 months in length.

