5.3 Interruption due to COVID-19 Pandemic

The intervention period for BEAGLE was originally slated to begin in April 2020. However, on March 21, 2020, the governor of Illinois and mayor of Chicago issued a “stay-at-home” order to mitigate harm from the COVID-19 pandemic. This severely impacted regular primary care activities at Northwestern Medicine. As such, we chose to delay the start of the intervention until regular care resumed. The intervention was rolled out on September 1, 2020, and the look-back period for the study measures was adjusted to exclude data collected between March 1, 2020 and August 31, 2020. So, for example, study outcomes reported in December 2020 included the following 12 months of data: June 1, 2019 – February 29, 2020 plus September 1, 2020 – November 30, 2020.

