6.2 Secondary endpoints

We chose secondary endpoints related to the primary PSA, UA/UC, and DM outcomes. These were selected to identify other burdens on the healthcare system, and included:

- PSA
 - Prostate biopsy in older men
 - Prostate MRI in older men
 - New prostate cancer diagnosis in older men
- UA/UC
 - Total urinalysis use in women aged 65 and older
 - Total urine culture use in women age 65 and older
 - Antibiotic treatment in women age 65 and older (all oral UTI treatments)
 - Antibiotic treatment in women age 65 and older (nitrofurantoin and Fosfomycin only)
 - C. difficile infection in women age 65 and older

- Rash in women age 65 and older
- DM
 - Hypoglycemia requiring an urgent care visit (not emergency department) among eligible patients

We will also measure the three co-primary outcomes monthly during a follow-up period (months 19-30) to evaluate the persistence of any effects observed during the study period.

We will survey the clinicians who consent to participate in an online questionnaire about their attitudes about their experience with study interventions as well as their attitudes and beliefs about testing and treatment more broadly among geriatrics patients. See Baseline Clinician Survey and Follow-up Clinician Survey.

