7. STUDY PROCEDURES

7.1 Schedule of Evaluations

Assessments	Historical practice: Baseline overuse (Month - 17 to Month 0)	Baseline, Enrollment, Randomization (Month 0, Day 1)	Intervention Start (Month 1)	Monitored and Measured Monthly	Intervention End (Month 18)	Follow-up Period (Month 19 to Month 30)
Clinician-level Assessments						
Informed Consent		X				
Demographics		X				
Inclusion/Exclusion	X					
Provider Attitudes Survey		X			X	
Patient-level Assessments						
ICD-10 codes	X	X	X	X	X	X
Ordering	X	X	X	X	X	X
Adverse Events	X		X	X	X	

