10.4.2. Secondary and safety outcomes

The secondary outcomes related to the primary PSA, UA/UC, and DM outcomes included:

- PSA
 - Prostate biopsy in older men
 - Prostate MRI in older men
 - New prostate cancer diagnosis in older men

- UA/UC
 - Total urinalysis use in women aged 65 and older
 - Total urine culture use in women age 65 and older
 - Antibiotic treatment in women age 65 and older (all oral UTI treatments)
 - Antibiotic treatment in women age 65 and older (nitrofurantoin and Fosfomycin only)
 - C. difficile infection in women age 65 and older
 - Rash in women age 65 and older
- DM
 - Hypoglycemia requiring an urgent care visit (not emergency department) among eligible patients

We will also measure the three co-primary outcomes monthly during a follow-up period (months 19-30) to evaluate the persistence of any effects observed during the study period.

We did not study any safety endpoints related to the PSA primary outcome. The safety endpoints related to the UA/UC and DM primary outcomes were deemed serious adverse events, and included:

- EHR-identified ED or hospital care possibly due to UTI or sepsis among women 65 and over following an office visit
- EHR-Identified ED or hospital care possibly due to hyperglycemia among previously tightly controlled
- Poor diabetes control ($\text{HbA1c} > 9\%$) among individuals who were previously tightly controlled ($\text{HbA1c} < 7\%$)

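### Section 5.2 promises all study outcomes to month 30, but no analysis of the safety endpoints is explicitly planned after month 18

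*Combined protocol and SAP*

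**What the plan says.** Two places point to a wide follow-up. Section 5.2 says: "We will continue to collect data on all study outcomes for 12 months after the intervention ends to measure persistence of effects". Section 1.2.2 plans to look at whether the effects found under Aim 1 persist, using a further 12 months of data. If Aim 1 is the primary aim of section 1.1, it covers indicators of patient safety as well as the quality measures.

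Four places point to a narrow one. The précis says "we will track all 3 co-primary outcomes for another 12 months after the intervention ceases". Sections 6.2 and 10.4.2 share a sentence that begins "We will also measure the three co-primary outcomes monthly during a follow-up period (months 19-30"; neither carries the secondary or safety outcomes into those months. In the section 7.1 schedule, the row "Adverse Events" is marked up to Intervention End (Month 18) and is blank in the follow-up column, whereas ICD-10 codes and ordering are marked there.

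Sections 8 and 10.4.2 class the UA/UC and DM safety endpoints as serious adverse events, so the blank row is the one that covers them. They are ED or hospital care possibly due to UTI or sepsis, ED or hospital care possibly due to hyperglycemia in previously tightly controlled patients, and HbA1c above 9% in patients previously below 7%.

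**The concern.** The alerts stop at month 18, but the consequences of decisions made under them need not. Section 5.1 says the diabetes alert encourages the clinician to decrease medication. A reduction made late in the intervention period might be followed by a raised HbA1c, or by hyperglycemia care, only after month 18. The follow-up period also exists to test whether the changed behavior continues. If it does, further reductions will occur in months 19 to 30.

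Under the narrow reading, the trial would report the intended effect to month 30 and the harms only to month 18. It could then say that a reduction persisted, but it would have no planned results on whether the persistent reduction was also safe. The secondary outcomes have the same mismatch, since 5.2 includes them and 6.2 and 10.4.2 do not carry them forward.

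**Working it through.** **1. Calendar.** Section 5.3: "The intervention was rolled out on September 1, 2020". Section 5.2: "The intervention period will be 18 months in length for all participants".

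- 1 September 2020 + 18 months: month 18 ends 28 February 2022.
- + 12 months: month 30 ends 28 February 2023.

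This reproduces the end of the data window in section 4.2 (February 28, 2023). The gap in scheduled adverse-event capture is therefore exactly the 12 follow-up months.

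**2. Is the blank cell a broken table?** Each patient-level row in 7.1 has a label and six cells:

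| Row | Historical | Baseline | Start | Monthly | Month 18 | Months 19–30 |
|---|---|---|---|---|---|---|
| ICD-10 codes | X | X | X | X | X | X |
| Ordering | X | X | X | X | X | X |
| Adverse Events | X | blank | X | X | X | blank |

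The adverse-event row has the same number of cells as the others, so the blank is not a column shift.

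**3. Does another section plan the analysis?** Section 10.5 treats the secondary and safety outcomes like the co-primaries, in a model whose time period is historical baseline versus intervention. Its fallback for rare events is one pull for each of those two periods, with none for follow-up. This silence is not decisive alone, because 10.5 gives no follow-up term for the co-primaries either. What separates the two sets of outcomes is that the précis, 6.2 and 10.4.2 name the co-primaries for months 19 to 30 and nothing else. The last scheduled DSMB meeting (10.3) is at the end of the intervention period.

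**4. Planned safety observation after a medication change.** For a change in month m, the whole months left are 18 − m under the schedule and 30 − m if capture runs to month 30.

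| Month of change | To month 18 | To month 30 |
|---|---|---|
| 13 | 5 | 17 |
| 18 | 0 | 12 |
| 19 | none | 11 |
| 30 | none | 0 |

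Months 13 to 18 are 6/18, or one third, of the intervention period in calendar time. The documents do not say when reductions occur, so this is not a share of reductions; in principle that share could lie anywhere between none and all. As an illustration only, suppose reductions are spread evenly over the 18 months:

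- under 3 months of observation: 3/18 = 16.7%
- under 6 months: 6/18 = 33.3%
- under 12 months: 12/18 = 66.7%
- mean observation: 9 months to month 18, against 9 + 12 = 21 months to month 30

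With capture to month 30 the three shares are 0%, because even a change at the end of month 18 has 12 months left. Reductions clustered early would lower the month-18 shares, and reductions clustered late would raise them.

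**The case against.** The best defense is that the narrow scope was deliberate. The 5.2 sentence ends with persistence as its purpose, and the précis, 6.2 and 10.4.2 tie persistence to the co-primaries. On that view the mention of all outcomes in 5.2 is loose wording, and extending safety analysis is a preference. This is a fair reading, but it still requires 5.2 to be corrected and 1.2.2 to be clarified.

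The opposite defense is that safety is already covered through 5.2 and 1.2.2. That may be what was intended, but no section says which safety analysis would be done for those months.

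Several stronger readings are tempting, and the documents do not support them:

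- *Delayed harm cannot be seen.* ICD-10 codes are scheduled for follow-up, section 11.2 plans an extract at its end, and the DM measure itself needs HbA1c. The endpoints could probably be derived without new data collection.
- *Safety oversight ends at month 18.* Sections 8 and 8.1 set no cutoff for reporting unanticipated events, and 10.3 allows extra DSMB meetings as needed.
- *One third of reductions are poorly observed.* One third is calendar time only.
- *The 365-day window implies a detection lag for HbA1c above 9%.* That window defines the co-primary measures; sections 8 and 10.4.2 give none for the safety endpoints.
- *The trial will claim that persistent reduction is safe.* No section says so.

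**Conclusion.** The inconsistency is real and lies in current text, but it is minor. Sections 5.2 and 1.2.2 can be read as carrying safety to month 30; the précis, 6.2, 7.1 and 10.4.2 do not carry it past month 18. As written, no analysis of the safety endpoints is explicitly planned for the 12 follow-up months.

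If the narrow sections govern, medication changes in months 13 to 18 have under 6 months of planned safety observation and those in months 19 to 30 have none. The number of patients or events affected cannot be given, because the documents report neither the timing of reductions nor the event rates. The 18-month safety comparison between randomized arms and the primary analysis are unaffected. The conclusion rests on reading the adverse-event row as the one that covers the section 8 endpoints, which their classification supports.

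**What to change.** Reconcile 1.2.2, 5.2, 6.2, 7.1 and 10.4.2 on which outcomes are analyzed in months 19 to 30. Preferably, run the section 8 safety query through month 30 in the end-of-follow-up extract that section 11.2 already plans, and report it by randomized arm for months 19 to 30, separately from the 18-month safety comparison. State in 10.5 how that period is analyzed. Specify the query before identifiers are destroyed, which the privacy text in section 12 ties to completed analytic files and accepted manuscripts.

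If this is not done, narrow 5.2 to the co-primary outcomes, clarify 1.2.2 to match, and state in the report that safety was assessed only to month 18.

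This is a cheap improvement: a longer date range in a query that is needed anyway. The downside is one more table, with mixed on- and off-alert exposure to explain. Changes made late in follow-up would still have little observation, from 11 months down to 0, and the table should say so.
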